**CONFIDENTIAL**

Project No. BLI-1005-002

Statistical Analysis Plan for PDC-1421

“Final” Page 25 of 34

Protocol Version: 2.3

SAP Version: 20180626\_01

Category 5 – Active Suicidal Ideation with Specific Plan and Intent

Category 6 – Preparatory Acts or Behavior

Category 7 – Aborted Attempt

Category 8 – Interrupted Attempt

Category 9 – Actual Attempt (non-fatal)

Category 10 – Completed Suicide

Suicidal ideation is identified if the total score of the five suicidal ideation questions (Categories 1-5)>0. Suicidal behavior is identified if the total score of the five suicidal behavior questions (Categories 6-10)>0. Suicidal ideation or behavior is identified if the total score of the ten suicidal ideation and behavior questions (Categories 1-10)>0.

Changes of suicidal ideation, suicidal behavior, and suicidal ideation or behavior from baseline during treatment will be summarized in a shift-table by visit, center and treatment.

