4.2 Exclusion Criteria

1. Have a current or previous major psychiatric disorders which be defined to be per the DSM-IV-TR, including obsessive-compulsive disorder, posttraumatic stress disorder, bipolar I or II, manic or hypomanic episode, schizophrenia, major Axis II disorders which might compromise the study, and major depression with psychotic symptoms, mental retardation.
2. Use of any treatment for MDD in the last 2 weeks before visit 1 (4 weeks for fluoxetine).
3. Use of psychoactive drugs within the last 2 weeks before visit 1 other than that subjects had insomnia who need the treatment as determined by the Investigator.
4. Subjects who were non-responsive to two or more courses of antidepressant medications given an adequate dosage* for symptom treatment within four weeks, or by the judgment of the investigator considered to have treatment resistant depression (TRD), or a history of electroconvulsive therapy (ECT), transcranial magnetic stimulation (TMS) or psychosurgery within the last year.
5. Have a history of any seizure disorder.
6. Any clinically significant abnormal vital sign, ECG, laboratory values as determined by the investigator which might interfere with the study.

7. Any organic disorder caused medical related depression which cannot be under well-controlled such as clinically significant in neurological, gastrointestinal, renal, hepatic, cardiovascular, respiratory, metabolic, endocrine, hematological or other major disorders.
8. Have a high suicidal risk as measured by MINI.
9. Have a history of substance dependence/abuse** within the past 6 months or any positive drug screen result is determined to be caused by subject's drug abuse at visit 1.
10. Have a history of severe allergies to more than 1 class of medication or multiple adverse drug reactions.

* The adequate dosage of the antidepressant medication is defined as the average of the usual dose (mg/day) recommended in American Psychiatric Association (APA) Practice Guideline for the Treatment of Patients with Major Depressive Disorder, Third Edition. E.g. the usual dose of Citalopram is 20-60 mg/day, the adequate dosage is 40 mg/day.

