**Secondary endpoints are:**

- MADRS total score—change from baseline to week 2 and 7
- HAM-D-17, CGI, DSSS and HAM-A—change from baseline to week 2, 4, 6 and 7
- Percentage of partial responders and responders (defined as participants with a 25-50% decrease and a  $\geq 50\%$  decrease from baseline in total score, respectively) in MADRS total score by Week 2, 4, 6 and 7
- Difference in the mean changes of MADRS, HAM-D-17, HAM-A, DSSS, CGI and C-SSRS from baseline to week 2, 4, 6 and 7 between PDC-1421 Capsule and placebo groups.

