### **6.5.7 *C-SSRS***

Results of C-SSRS will be presented by part, center, visit, and treatment. The baseline of C-SSRS was set at screening visit (Visit 1).

The analysis for C-SSRS will follow the official guidance “Columbia-Suicide Severity Rating Scale - Scoring and Data Analysis Guide.” The 10 categories will be defined according to 10 binary responses (yes/no) on the C-SSRS, which are:

Category 1 – Wish to be Dead

Category 2 – Non-specific Active Suicidal Thoughts

Category 3 – Active Suicidal Ideation with Any Methods (Not Plan) without Intent to Act

Category 4 – Active Suicidal Ideation with Some Intent to Act, without Specific Plan

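### The C-SSRS shift table in SAP 6.5.7 is built on yes/no flags, so escalation within suicidal ideation is tabulated as no change

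*SAP*

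**What the plan says.** SAP 6.5.7 refers to a published C-SSRS scoring guide and starts from single items: "The 10 categories will be defined according to 10 binary responses (yes/no) on the C-SSRS". The ideation items run from "Category 1 – Wish to be Dead" to "Category 5 – Active Suicidal Ideation with Specific Plan and Intent". Categories 6 to 10 cover behavior.

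The section then forms three flags. For ideation: "Suicidal ideation is identified if the total score of the five suicidal ideation questions (Categories 1-5)>0". For behavior: "Suicidal behavior is identified if the total score of the five suicidal behavior questions (Categories 6-10)>0". The third flag is yes if any of the ten items is yes. The change analysis uses these flags: "Changes of suicidal ideation, suicidal behavior, and suicidal ideation or behavior from baseline during treatment will be summarized in a shift-table", split by visit, site and arm.

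Four other places bear on the point.
- SAP 6.5.7 also promises C-SSRS results for each study part, site, visit and arm, without naming the statistics.
- SAP 6.5.7 takes Visit 1 as the C-SSRS baseline. Protocol 7.2 takes the pre-dose Visit 2 data as the safety baseline.
- SAP 5.3.2 lists as a secondary endpoint "Difference in the mean changes of MADRS, HAM-D-17, HAM-A, DSSS, CGI and C-SSRS", and Protocol Table 12 (item 5) does the same. No C-SSRS score is defined for it, and SAP 6.4.2 leaves C-SSRS out when it names the group differences.
- Protocol 4.2, item 8, excludes patients who "Have a high suicidal risk as measured by MINI". Lower levels of risk are not excluded.

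**The concern.** The C-SSRS items separate a passive wish from active ideation with a plan. Reducing them to present or absent before computing change discards that distinction at the step where it matters. A patient whose ideation flag is already yes at baseline can only stay yes or become no, so the ideation table can show improvement to none but no deterioration.

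The C-SSRS is a named safety parameter (Protocol 7.1, SAP 5.3.2) in a depression trial. A table with no adverse shifts could be read as showing no worsening, when it would look the same if some patients had moved from Category 1 to Category 5. The SAP treats other safety data more finely: for physical examination and ECG, its transition tables separate clinically significant from non-significant findings (SAP 6.5.4 and 6.5.6).

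**Working it through.** The documents state no figure to reproduce here. The check applies the SAP's own rules to example patients and then counts which shifts can appear.

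**Inputs (SAP 6.5.7).** Ten items c1 to c10, each 0 or 1.
- Ideation flag: I = yes if c1 + c2 + c3 + c4 + c5 > 0
- Behavior flag: B = yes if c6 + c7 + c8 + c9 + c10 > 0
- Either flag: E = yes if c1 + ... + c10 > 0

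**Step 1. Escalation within ideation.**

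| State | Sum 1-5 | Sum 6-10 | I | B | E |
|---|---|---|---|---|---|
| Baseline: Category 1 only | 1 | 0 | yes | no | yes |
| Later: Category 5 only | 1 | 0 | yes | no | yes |
| Later: Categories 1, 2 and 5 | 3 | 0 | yes | no | yes |
| Later: Categories 1 to 5 | 5 | 0 | yes | no | yes |

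All three later states give the same flags as baseline. The patient is yes/yes, no/no and yes/yes, unchanged in every table. In the second row even the raw sum does not move, so tabulating the sum would not be a safe repair.

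**Step 2. How many shifts are hidden.** Let the ideation level be the most severe category endorsed, from 0 (none) to 5.
- Possible worsening shifts: 5 + 4 + 3 + 2 + 1 = 15
- Shown by the yes/no table (from 0 to any of 1-5): 5
- Hidden in the yes/yes cell (from 1, 2, 3 or 4 upward): 4 + 3 + 2 + 1 = 10

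The same holds for improvement: of 15 possible shifts, only the 5 that end at 0 appear. These are counts of table cells, not of expected patients.

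**Step 3. New behavior.** Take a baseline of Category 1 only, and a later visit with Categories 1 and 6. I stays yes and E stays yes, but B goes from no to yes. This worsening is visible, so the masking is confined to movement within ideation.

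**Step 4. How many patients could be affected.** The documents give no rate of baseline ideation. Part II has 60 patients in three equal arms, 20 per arm. Purely as an assumption, if 30% to 60% have a yes at baseline, then 20 x 0.30 = 6 to 20 x 0.60 = 12 patients per arm start in a position where worsening ideation cannot register. That is the number exposed to the problem, not the number who would worsen, which is unknown and could be zero.

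**The case against.** A reader might infer that the plan contains no analysis of change in C-SSRS severity, or that it cannot detect worsening in anyone who enters with ideation. The documents do not support either reading.
- The behavior flag has its own shift table, so a patient with baseline ideation who progresses to preparatory acts or an attempt is picked up (step 3).
- The category data are not lost. By-visit C-SSRS results are promised, and counts per category are a natural reading. They would show a Category 5 case, though not that patient's movement from baseline.
- A between-arm mean change in C-SSRS is still a listed endpoint. It lacks a defined score, which is a different defect from having no analysis.
- The scoring guide cited in SAP 6.5.7 and the mock-up tables cited in SAP 11.3 were not available. Either might contain a finer table.
- Clinically significant findings can be recorded as adverse events (Protocol 7.3), and serious events are narrated (Protocol 8.3). A serious escalation could surface there, although that depends on investigator judgment.

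It is also fair to say that a by-visit shift table is a legitimate display; a worst post-baseline column is an addition, not the correction of an error.

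These objections limit the point but do not remove it. None of these routes is a commitment in the SAP text to compare a patient's ideation severity with baseline once ideation is already present.

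**Conclusion.** The point holds for the shift table. As SAP 6.5.7 is written, escalation within Categories 1-5 is tabulated as unchanged in any patient who enters with ideation: 10 of 15 possible worsening shifts are hidden, including Category 1 to Category 5. The SAP text commits to no other analysis that would show such worsening.

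This rests on a literal reading of the flag rules and on reading Categories 1 to 5 as increasing in severity, which their labels imply but the SAP does not state. That patients with milder ideation can enter follows from the exclusion criterion; how many do is unknown. The guide or mock-up tables could already contain the missing table, in which case only the SAP wording needs to catch up. The primary efficacy analysis is not affected. The change is worth making because it is cheap and concerns a named safety parameter.

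**What to change.** In SAP 6.5.7:
1. Reconcile the C-SSRS baseline first. SAP 6.5.7 and Protocol 7.2 name different visits, and every shift depends on the choice.
2. Keep the three yes/no shift tables.
3. Add a shift table of the most severe ideation category (0 = none, then 1-5): baseline against each visit, and baseline against the worst post-baseline value.
4. Show behavior (Categories 6-10) separately, and do not merge it with ideation into one 0-10 maximum. On a merged scale a patient with Category 6 at baseline whose ideation goes from 1 to 5 would still have a maximum of 6 and again appear unchanged. Nor do the documents say that Categories 6-10 are ordered by severity.
5. Report per arm the number and percent of patients with new ideation, with an increase in ideation category, and with new behavior.
6. State that the C-SSRS mean-change item has no defined score and that C-SSRS change will be reported through these tables. SAP 5.4 says that all analyses follow the protocol, so note the clarification there too.

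The cost is an SAP revision, matching mock-ups, and one or two extra tables with small counts. No new data are needed: Part II already schedules the C-SSRS at Visits 1 to 6 (Protocol Table 16), and the SAP already defines the ten responses. Made in the SAP, the change leaves Protocol Table 12 as it stands. Replacing the endpoint there would call for a written protocol amendment under Protocol 10.2, which this fix does not require.

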## **6.6 Statistical / Analytical Issues**

### ***6.6.1 Adjustments for covariates***

No adjustment for covariates will be performed in this study.

### ***6.6.2 Handling of Dropouts or Missing Data***

Missing data caused by premature termination will be utilized the last observation carried forward (LOCF). However, the LOCF method will only be applied to data on efficacy. No imputation will be done for safety data.

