8.3 Analysis of Efficacy and Safety

The efficacy measures are conducted on the per-protocol (PP) and intent-to-treat (ITT) basis. The per protocol will be defined as (1) The drug compliance is at least 80% (2) Subjects have completed data to determine the primary endpoint. (3) Subjects cannot have protocol deviation. The protocol deviation will be defined as (1) Inclusion or exclusion criteria not satisfied. (2) Not permitted concomitant medications (3) Wrong randomized treatment prescribed. An intent-to-treat (ITT) basis will be defined as the data are analyzed by the treatment groups to which the randomized patients who take at least one dose of study medication and have any post-baseline safety data collected. The safety measures are conducted on the ITT basis. The data are analyzed utilizing the last observation carried forward (LOCF) technique to impute the missing data.

The efficacy and safety information recorded on CRF will be summarized by tables presented in frequency and percentage for categorical variables, in mean with SD as well as median with the minimum and maximum for continuous variables. The comparison between three groups will be analyzed by nonparametric method as appropriate. All adverse events will be summarized with coding term, severity, relationship to study drug by frequency tables with the counts and percentage. In addition, serious adverse events will be listed with event narration.

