8.4 Premature Termination and Handling of Missing Data

Any premature termination of the study therapy will be recorded in CRF. Listing of the subjects with premature termination will be provided with the dates and reasons. Missing data caused by premature termination will be utilized the last observation carried forward (LOCF).

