#### **5.4 Changes in the Conduct of the Study or Planned Analyses**

All the statistical analysis will follow protocolized statistical contents.

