### **6.5.3 *Laboratory data***

Descriptive statistics of original data and net changes in hematology and biochemistry data will be presented by part, center, visit, and treatment.

Results of clinical significance with regard to laboratory data will be summarized with frequency and percentage.

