### **6.5.5 *Vital Signs***

Descriptive statistics of net changes in vital signs including systolic and diastolic blood pressure, heart rate and body temperature will be presented by part, center, visit, and treatment.

Results of clinical significance with regard to vital sign will be summarized with frequency and percentage.

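### Protocol and SAP disagree on LOCF for safety data, and the visible by-visit laboratory and vital-sign summaries do not carry early leavers' changes into later visits

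*SAP*

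**What the plan says.** **Protocol.** Section 8.3 sets the safety population: "The safety measures are conducted on the ITT basis". Its next sentence gives the missing-data rule: "The data are analyzed utilizing the last observation carried forward (LOCF) technique to impute the missing data". Nothing there confines the rule to efficacy. Section 8.4 repeats LOCF for data lost through premature termination, again without restriction.

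**SAP.** Section 5.3.1 repeats the protocol's population paragraph but stops before its LOCF sentence. Section 6.6.2 restates the 8.4 rule and then narrows it: "However, the LOCF method will only be applied to data on efficacy". It adds: "No imputation will be done for safety data". Section 5.4, the place for changes to planned analyses, declares none: "All the statistical analysis will follow protocolized statistical contents". The table of SAP changes in 11.5 has no entry on this either.

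**Safety displays.** For laboratory values, SAP 6.5.3 plans: "Descriptive statistics of original data and net changes in hematology and biochemistry data will be presented by part, center, visit, and treatment". For vital signs, 6.5.5 plans net changes, where "heart rate and body temperature will be presented by part, center, visit, and treatment". Both sections add a frequency and percentage of clinically significant results, without saying at which visit or over what period. The visible text specifies no change to the last on-treatment value and no worst-value summary.

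**The concern.** Two things look wrong, and they differ in weight.

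The first is a plain inconsistency. Someone programming from the protocol would fill the week-6 safety rows by LOCF; someone programming from the SAP would leave them as observed. SAP 5.4 tells the reader that no such difference exists.

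The second is what remains once LOCF is set aside. A patient who stops after week 2 contributes a laboratory and vital-sign change at week 2 and none at weeks 4 and 6. If leaving is related to the change itself, the later rows show a smaller mean change than the treated group experienced. The variables concerned are ones the protocol singles out. Section 1.4.1 names fluctuating electrolytes as a potential risk, reports lower heart rate and diastolic pressure in the dog telemetry study, and says the cardiovascular system will be monitored. Part II compares two doses with placebo, so the size of such changes by arm bears on how the doses are described.

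**Working it through.** No sample size, power or alpha figure is involved, so there is no stated figure to reproduce. The check is a comparison of the texts plus two small illustrations.

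**1. The rules side by side**

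| Place | Rule | Scope |
|---|---|---|
| Protocol 8.3 | LOCF | the data; follows directly on the safety-population sentence |
| Protocol 8.4 | LOCF after premature termination | not limited |
| SAP 6.6.2 | LOCF | efficacy only; none for safety |
| SAP 5.4 | no change from protocol | all analyses |

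Even if the sentence in Protocol 8.3 is read as meant for efficacy, the unrestricted rule in 8.4 still conflicts with SAP 6.6.2.

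**2. How many patients a week-6 row holds**

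Part II randomises 60 patients 1:1:1, so 60 / 3 = 20 per arm. Dropout d is an assumption. The observed-case count at week 6 is 20 × (1 − d):

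- d = 5%: 19
- d = 10%: 18
- d = 20%: 16
- d = 30%: 14

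A row built on each patient's last or worst on-treatment value holds every treated patient with at least one such value, so up to 20.

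The displays are also split by centre. SAP 6.6.4 names six centres, and SAP section 4 says one enrolled nobody. If enrolment were even, 20 / 5 = 4 patients per arm per centre, and one leaver would be a quarter of a cell. SAP 6.6.8 states pooling of centres only for efficacy.

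**3. What the mean change could look like (illustration only)**

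Assume completers' mean heart-rate change is −1 bpm and leavers had a mean of m at their last on-treatment visit, with every leaver having such a value. The observed-case week-6 row shows −1 whatever d is. The mean of last on-treatment values is (1 − d) × (−1) + d × m.

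With m = −12:

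- d = 10%: −0.9 − 1.2 = −2.1
- d = 20%: −0.8 − 2.4 = −3.2
- d = 30%: −0.7 − 3.6 = −4.3

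The mildest case tried (m = −8, d = 10%) gives −0.9 − 0.8 = −1.7. The most severe (m = −15, d = 30%) gives −0.7 − 4.5 = −5.2. If leavers resemble completers (m = −1), the result is −1 for every d and nothing is hidden.

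Under the same assumptions, the protocol's LOCF would put these values in the week-6 row, where the SAP puts −1. That is the sense in which the two documents give different tables.

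**The case against.** The strongest reply is that a patient who stops because of an effect is already visible elsewhere, and most of this stands.

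- Protocol 7.3 makes clinically significant abnormal findings adverse events, including those that lead to withdrawal. SAP 6.5.1 tabulates treatment-emergent events by arm with severity, action taken, relationship and outcome. SAP 9.2 tabulates withdrawal reasons, and Protocol 8.4 lists premature terminations with dates and reasons. Gastrointestinal effects appear mainly as adverse events.
- SAP 6.1 calls for sample size, minimum and maximum for continuous variables, so a falling n and the extremes at earlier visits can be seen. The schedules of assessments show no early-termination visit, so a leaver's last on-treatment value usually sits in an earlier by-visit row already.
- Not imputing by-visit safety values is sound practice. LOCF would present a week-2 value as a week-6 value.

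A reader might infer that affected patients disappear from the safety evaluation; the sections above show that they do not. A reader might also infer that the SAP concealed the change. It did not: 6.6.2 states the rule openly, and the fault is that 5.4 says the opposite. Nor can one conclude that the plan contains no last-value summary at all. The mock-up tables are a separate attachment (SAP 11.3) and SAP 6.6.9 on visit windows was not available, so neither could be checked.

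What the reply does not remove is the contradiction, or the fact that the by-visit rows give no per-arm summary of change that includes every treated patient with data. Clinical-significance counts rest on judgement and do not show the size of a change.

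**Conclusion.** The point holds in a limited form. Protocol 8.3 and 8.4 conflict with SAP 6.6.2, and the statement in SAP 5.4 that all analyses follow the protocol is wrong on this matter. Dropping LOCF for safety is acceptable. The practical loss is confined to the size of laboratory and vital-sign changes in patients who leave early; a patient who misses a single visit is likewise absent from that visit's row. Overt events remain captured, and the primary MADRS analysis is not touched.

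The size is unknown. The documents give neither a dropout rate nor leavers' values, so the heart-rate range of −1.7 to −5.2 against −1 bpm is conditional on leavers having larger changes. It must not be read as an estimate that the later tables understate an effect; if leavers resemble completers there is no understatement. The dog findings themselves are described in Protocol 1.4.1 as mild, not clinically significant and seen only at 2500 mg/kg. The conclusion on missing summaries is limited to the visible SAP text.

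**What to change.** 1. State in SAP 5.4 that the LOCF rule in Protocol 8.3 and 8.4 does not apply to safety data, and reconcile the two documents so that one rule stands.
2. Keep the by-visit laboratory and vital-sign tables on observed data, with n shown at each visit.
3. Unless the mock-up tables already contain them, add for each laboratory and vital-sign variable, by part and arm with centres pooled, the change from baseline to the last on-treatment value and to the worst on-treatment value.
4. Define the direction of worst for each variable. Where a variable can be abnormal either way (for example sodium, potassium, calcium, heart rate, blood pressure), report both the minimum and the maximum.
5. Exclude the off-drug follow-up visit (week 5 in Part I, week 7 in Part II) from these summaries.

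The cost is SAP wording and a little more analysis work on data already collected. The downside is slightly longer tables.
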